Official Title: CCMs among Hispanic Population Study group (CHIPS)

NCT number: NA (Pending)

Date: 11/3/2021

Protocol/Research Activity Plan

A. Review of prior work in the area

Genetic contributions to major forms of cerebral cavernous malformations (CCMs) have been recognized for a long time, however, many causative factors for cerebral cavernous malformations have yet to be determined. CCMs were initially identified as a genetic defect among Hispanic patients ¹ and, to date, remain a major neurological disorder among Hispanic populations with the highest prevalence compared to other ethnic groups ²⁻⁴. Despite these overwhelming statistics, only three loci have been identified in CCM patients (CCM1-3)^{2, 5-11}, with many patients still harboring unidentified mutations ¹². The proposed research will be focused on the elucidation of causative factors and diagnostic biomarkers for cerebral cavernous malformations by the **CCMs among Hispanic Population Study group (CHIPS)**, which is composed of several basic scientists, neurologists, and neurosurgeons.

B. Specific Objectives

The objective of this research is to identify new genetic loci and validate novel serum biomarkers we recently identified for CCMs and other types of hemorrhage strokes in humans. The purpose of the study is to identify and validate the causative factors and prognostic biomarkers for hemorrhagic strokes in humans. Recently, a team led by our research co-PI has made some breakthrough findings involving new serum biomarkers for predicting CCMs hemorrhagic events (TTU has filed provisional patent). Our data (from IACUC 18004-submitted and in peer review) demonstrated that there is a correlation between serum levels of Progesterone (PRG) and the initiation of hemorrhagic strokes in Ccms mutant mice. Furthermore, four more biomarkers (Serpin A6, IL-12, IL-6, and Albumin) are all associated with PRG homeostasis/biogenesis in serum, and also correlate well with hemorrhagic events in Ccms mutant mice. This research is especially significant for this region which contains the highest percentage of Hispanics in the nation (>80% of the entire population), recognizing El Paso as the epicenter for CCMs by stroke clinicians around the world. As such, this proposed project has regional relevance and importance in rural health disparities on the U.S.-Mexico border region.

C. Hypothesis

We hypothesize that there are additional causative genetic loci contributions to the pathogenesis of human cerebral cavernous malformations and conformation of effective serum biomarkers for diagnostic and pragmatic use will be an essential tool to prevent hemorrhagic CCMs in humans. We will use our collected patient samples from local Hispanic populations for next-generation-sequencing (NGS) and biomarker assays.

D. Study Design

Patient recruitment and clinical data acquisition

Clinical and translational research will be structured to assess potential biomarkers and heritable factors for hemorrhagic CCMs. Up to 900 CCM Patients (between both Standard of Care and Research only samples) will be identified from participating clinical co-PI (Principle Investigators) practices to investigate the risk factors and hemorrhage incidence rates among the Hispanic population. All patients will be asked to invite their relatives for the possibility of participation in this study by providing a flyer to the subject to give to their relatives, and if they are interested, the relative may contact the research PI or Clinical co-PI's to participate in this study and provide consent. Non-English speaking participants will be provided all documents in Spanish, and will also be consented, in English or Spanish.

Demographic details of patients will be recorded as well. Potential subjects will be identified using the following criteria:

1. Having a positive medical history associated with CCMs, or stroke/epilepsy
2. Having a family member with a positive medical history associated with CCMs, or stroke/epilepsy

Clinical co-PIs and co-investigators will describe in detail the clinical presentations associated with CCMs, or stroke/epilepsy, and the study procedures for an initial screening. If the potential subject agrees to participate in the initial screening, informed consent and/or assent will be obtained by the Clinical co-PIs or co-investigators and/or approved research personnel working on the study. Consenting will occur in the PFS and Laboratory suite located at University Medical Center of El Paso, 1st floor UMC main building, [name]. Alternatively, if this location is not available for consenting patients, we will consent patients in private, closed-door conference rooms that can be reserved for CONSENTING ONLY. These rooms are located in MSBI rooms #2106, 3106 and 4106 located at [name]. No other research procedures pertaining to this study will occur in these rooms other than consenting patients. Once consent has been obtained, information gathered from the initial screening will be cross-examined with electronic and paper medical records to confirm their charted medical history. All patients who do not meet eligibility criteria will be excluded from participating in the study. After study criteria have been met, all subjects will have blood taken from one of the arm veins, as part of standard of care, with an additional one and a half tablespoons (2 vials, one for serum collection and one for plasma) being drawn for this study for genetic testing and validation analysis by research co-PI. All samples provided will be coded for confidentiality and privacy. The biological molecules (nucleic acid and proteins) obtained from the sample will be frozen and stored for future use. Completion of the questionnaire and the blood draw should take less than 30 minutes of the subject's time and will be completed in one visit. A blood draw is normally a routine part of the standard of care, for diagnosing and initial evaluation of stroke/epilepsy and CCM diagnosis.

In the unique circumstances where blood draws are not required for standard of care, one-and-a-half tablespoons of blood (2 vials, one for serum collection and one for plasma) will be extracted for genetic testing and validation analysis by research co-PI for this study with the following modifications from the standard procedure.

1. Up to 900 CCM Patients (between both Standard of Care and Research only samples), will initially be asked if they would like to participate in this study if they meet the inclusion criteria.
2. Primary care physicians on this protocol (Drs. [name], [name], [name], [name], [name], [name]) will be able to perform an electronic medical search of their patients to identify patients that were previously diagnosed with CCMs in the past 10 years (1/1/2011-1/1/2021). Primary Care physicians may ask currently approved research personnel to assist them with this task. Medical records will only be assessed to confirm ICD9/10 codes for their patients to confirm eligibility requirements, and to obtain electronic mail addresses, phone numbers, and/or mailing address to contact/present their patients with the currently approved IRB recruitment flyer/letter so they can decide if they would like to participate.
3. Any Patients that qualify to participate upon a medical search review by their primary care physician, would still be contacted and presented with our IRB approved recruitment flyer so that they can decide on whether they would like to participate. If these patients are interested in participating, they will be consented, as normal, and blood draw performed, as normal.
4. Alternatively, patients may contact either [name] or [name] to see if they qualify to participate in the study (based off the inclusion criteria) from posted notices of solicitation and recruitment flyers posted at the following websites:

1. <https://www.angioma.org/biomarker-development-project-in-el-paso-seeking-participants/>
2. <https://elpaso.ttuhscc.edu/research/ccm-survey.aspx>
3. <https://elpaso.ttuhscc.edu/research/ccm-survey-spanish.aspx>

5. Patients participating in blood draw for research purposes only that were not recruited involving a UMC/TTUHSCEP physician may provide their medical records to either [name] or [name] at their discretion to help make the analysis of their blood donation more meaningful in terms of clinical symptoms associated with the scope of this study. All medical records will be stored according to the same HIPAA compliance and regulations as if those records were obtained from their direct PCP.

6. If the participant agrees to provide medical records, additional demographic information that will be obtained includes affected individuals, age of onset, ethnicity, gender, type of stroke, date of birth, treatments received. An assessment of the patient's current condition will be made by asking if the patient shows any signs of gait apraxia, cognitive deficiency, and seizures. Specific questions will be asked in order to evaluate physical, social, cognitive, and overall health.

7. Consent/blood draws will be in the PFS and Laboratory suite located at University Medical Center of El Paso, 1st floor UMC main building, [name]. Alternatively, if this location is not available for consenting patients, we will consent patients in private, closed-door conference rooms that can be reserved for CONSENTING ONLY. These rooms are located in MSBI rooms #2106, 3106 and 4106 located at [name]. No other research procedures pertaining to this study will occur in these rooms other than consenting patients

8. Patients will be walked over to the PFS and Laboratory suite by [name] or [name] where informed consent and/or assent will be conducted (if consenting was not already completed in MSBI 2106, 3106 or 4106) by either [name] or [name], followed by blood draw for research purposes only which will be handled by a phlebotomists working in the PFS and laboratory suite.

9. The PFS and Laboratory suite is both a research lab as well as having equipped stations where phlebotomy work can be safely performed. Having one site for both processes eases our workflow and limits the number of coordinators that need to be added to this study by using different locations for each process. As stated in the procedure section for "blood draw for research purposes only" in the study application, the patients/subjects will be personally escorted by [name] or [name] and will stay with the subjects until all assents/consents have been performed as well as completion of the blood draws. Once complete, [name] or [name] will transport the samples back to the lab where they will be processed, and Biological molecules obtained from this sample (Nucleic acid and proteins) will be stored in MSBI in our -80 freezers until ready for analysis. All samples provided will be coded for confidentiality and privacy. Completion of the questionnaire and the blood draw should take less than 30 minutes of the subject's time and will be completed in one visit.

A small group of subjects will be identified as high-risk for hemorrhage due to CCMs from the stroke/epilepsy clinics. If any imaging modality is performed to assess their CCMs, these will be

included in the research analyses. All safety precautions and confidentiality to the findings from the blood samples will be upheld at all times during the study.

For screening and enrollment purposes, we define hemorrhage from CCMs as evident from brain imaging. Whether it may cause neurologic deficits or not, the subject shall be included as part of the study, once they are diagnosed to have one or may cavernous malformations. Given the high morbidity and mortality of the disease, demographic information, age at the time of treatment, type of treatment, and treatment dates will be obtained for all individuals. All clinical data will be de-identified with numerical coding in accordance with personal health information (PHI) regulations and will be stored using Excel software with encryption and security codes on a PC in the CCMs among Hispanic Population Study group (CHIPS). Confidentiality of protected PHI in compliance with the Health Insurance Portability and Accountability Act (HIPAA) will be ensured by utilizing text encryption, password protection, and limited personnel involvement.

Both sporadic and familial cases of CCMs will be recruited for this study. If the patient has either a first, second, or third-degree relative with similar clinical conditions, then we will consider this patient as a familial stroke case. The demographic information that will be obtained includes affected individuals, age of onset, ethnicity, gender, type of stroke, date of birth, treatments received. An assessment of the patient's current condition will be made by asking if the patient shows any signs of gait apraxia, cognitive deficiency, and seizures. Specific questions will be asked to evaluate physical, social, cognitive, and overall health. Responses from mothers of the patients will be acquired if the patient is a child to maintain consistency. If the patient is a child, we will also ask if the patient has experienced any recent increased frequency of headaches, nausea, and vomiting, or engorgement of the scalp veins. We ask these latter questions because some of these patients might have been lost to follow-up before and we will redirect them to the attending neurologist's and neurosurgeon's office for scheduling of clinic appointments. For patients, or their family representative, who are unable to provide an adequate medical history, the patient's electronic and paper medical records will be used to supplement incomplete data parameters. All screened patients for whom data could not be completely confirmed by interview, electronic or paper medical records will be excluded from further analyses. Willing candidates with severe anemia or active allergies will be excluded from this study.

Eligibility Criteria/Subject Population

➤ Inclusion Criteria

1. 10 to 89 years of age
2. Medical history meets the criteria for the International Classification of Diseases diagnosis codes 10 (ICD-10) for cerebral cavernous malformations (CCMs) (Q28.3 or D18.02) or stroke/epilepsy.
3. Medical history meets the criteria for the International Classification of Diseases diagnosis codes 9 (ICD-9) for cerebral cavernous malformations (CCMs) (228.02) or stroke/epilepsy.

OR

1. Has a family member whose medical history meets the criteria for the *International Classification of Diseases* diagnosis codes for cerebral cavernous malformations (CCMs) (Q28.3 or D18.02 or 228.02) or stroke/epilepsy.
2. Has a relatively complete medical history that can be accurately confirmed by an interview or electronic and/or paper medical records
3. Hispanic and non-Hispanic Americans

 - (1) If CBC or CMP was not ordered for the patient, then, at minimum, ESR and CRP must demonstrate normal levels, allowing this sample to qualify as a healthy control.
 - (2) If a patient's PCP has ESR, CRP and CBC ordered, then all three of these tests must show normal healthy levels for this sample to qualify as a healthy control.
 - (3) If a patient's PCP had all 4 tests ordered (ESR, CRP, CBC and CMP) then all 4 panels must show normal healthy levels for the sample to qualify as a healthy control.

3. The biospecimens (blood tubes with various volumes, depending on standard of care laboratory tests performed) will be de-identified by [name] or [name] before leaving the PFS laboratory suite.
4. Information about biospecimens will be recorded in such a manner that the identity of the human subjects cannot readily be ascertained directly or through identifiers linked to the subjects, and we will not contact the subjects, or attempt to re-identify subjects.
5. The only information that will be collected is age (xx yrs), Sex (M/F), and ethnicity (White/Hispanic/Asian/African American, etc) so that it may be used for age/sex/ethnicity matching of our CCM patient samples.
6. [name] or [name] will transport the samples back to the lab where they will be processed, and Biological molecules obtained from this sample (Nucleic acid and proteins) will be stored in MSBI in our -80 freezers until ready for analysis.

Next-generation sequencing (NGS)

Most of our collected stroke (CCMs) families are small nuclear families, consisting of two or more affected siblings which resemble the genetic basis of common and complex genetic traits. Updated results suggest that rare variants may account for the “missing” heritability. Such rare variants may have a large effect as genetic risk factors for complex genetic diseases. Therefore, current challenges will be to define the genetic basis of ‘missing’ heritability.

Next-generation sequencing (NGS) technologies will enable us to identify all the causative variants including “rare variants”. It is anticipated that whole-genome sequencing (or exome sequencing) will make significant contributions to our understanding of the genetic etiologies that contribute to complex human disease ¹³. In this proposal, we hypothesize that due to the heterogeneous nature of CCMs, some causative alleles for CCMs are rare genetic variants located in the unknown genetic loci; furthermore, a common pathophysiological event during hemorrhagic initiation makes predicting hemorrhagic events possible with shared biomarkers. Although the genetic basis for the stroke is likely to be heterogeneous, there are certainly some genetic overlaps among different families. Therefore, the whole-exome sequencing at TTUHSC with Agilent Sure Select Human All Exon kit will be used to sequence serum samples to identify the causative genetic variants for CCMs/stroke/epilepsy.

Using this new NGS technology at TTUHSC genomic core, we have successfully generated the whole-genome sequencing (exome) data and performed analysis for three unrelated patients in our other genetic projects, which built a solid foundation for our future success of this proposed project. Bioinformatics analysis of the NGS data would be finished by the end of 2025.

There are implications related to knowledge of possible genetic information that may be obtained as a result of this study. These include knowledge of genetic mutations which may be shared with the patient, as well as significant risk factors for those who test positive for these gene mutations. Because of the potential of a genetic basis for genetic inheritance of CCMs, resources have been provided in a separate document for additional genetic screening, if desired, as well as resources for genetic counselling. All additional resources are the subject’s financial responsibility and are not associated with this study.

Serum/plasma biomarker discovery

The statistical analysis for a genetic mutation in the Hispanic population will be performed using SAS software with support from the Division of Biostatistics & Epidemiology at Texas Tech University Health Sciences Center in El Paso, Texas. To assess the familial aggregation of stroke among Hispanics, Odds ratios (OR) and their 95% confidence intervals (CI) will be calculated using stratified data analysis and unconditional logistic regression. Odds Ratio (OR) for risk of disease in first-degree relatives of an affected person to risks of disease in first degree relatives of an unaffected person. Let OR = ratio of the disease odds for first-degree relatives of an affected person to the disease odds for first-degree relatives of an unaffected person. This is the familial risk ratio for first degree relatives and is a measure of the strength of familial aggregation of the disease. Cox proportional hazard models will be used to estimate hazard ratios (HR) and 95% confidence intervals (CI) estimating the relative risk of stroke according to the exposure of interest. The cumulative incidence of stroke among first-degree relatives will also be estimated. All models will be adjusted for matching variables including age and gender. All p-values will be two-sided, with the significance level cutoff at $p < 0.05$.

7. Research Team of CCMs among Hispanic Population Study group (CHIPS)

The Research Team of CCMs among Hispanic Population Study group (CHIPS) is consist of both research and clinical co- Principle Investigators (**co-PIs**), co-investigators, research and clinical coordinators, and other staff team members.

Research co-PI: [name], ScD, email:[contact]

Clinical co-PI: [name] [name] (Neurology), email: [contact]

Co-investigators: [name] (Neurology), [name] (Pathology), [name]. (Neurology), [name]. (Radiology), [name]. (Neurology)

Research Coordinators: [name]. (research) email: [contact]

Research staff: [name], B.S. (research) email: [contact], [name], (UMC) email: [contact], [name] (PFSOM), email: [contact] [name] (PFSOM) email: [contact], [name] (GSBS) email: [contact], [name] (PFSOM) email: [contact], [name] (UMC) email: [contact]

D. References

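### The familial-aggregation odds ratio is defined against relatives of unaffected persons, but the design supplies no sound reference group for it

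*Protocol*

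**What the plan says.** The Statistical Analysis Strategy gives the aim as "To assess the familial aggregation of stroke among Hispanics". The OR is the "ratio of the disease odds for first-degree relatives of an affected person to the disease odds for first-degree relatives of an unaffected person". ORs and confidence intervals "will be calculated using stratified data analysis and unconditional logistic regression", with adjustment for matching variables including age and gender. Of the OR the text says: "This is the familial risk ratio for first degree relatives and is a measure of the strength of familial aggregation of the disease". The same section plans the cumulative incidence of stroke in first-degree relatives.

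Who can supply family data is settled elsewhere in the protocol:

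- **Enrolled subjects.** Under Data Collection Methods, information on relatives comes from interviews with subjects.
- **Entry without own disease.** The recruitment criteria in Study Design admit a person "Having a family member with a positive medical history associated with CCMs, or stroke/epilepsy". The inclusion criteria repeat this after the OR: "Has a family member whose medical history meets the criteria". No degree of kinship is required. One route is a flyer: "All patients will be asked to invite their relatives for the possibility of participation in this study".
- **Controls.** Under Acquisition of Control samples (items 4 and 5), the 1000 leftover specimens carry only age, sex and ethnicity, and the donors will not be contacted or re-identified.
- **Cases.** Sporadic and familial cases are both recruited. A case counts as familial "If the patient has either a first, second, or third-degree relative with similar clinical conditions". The sequencing section says that most families collected so far have at least two affected siblings.

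**The concern.** A familial OR is interpretable only if the unaffected index persons were not chosen because of disease in their families, or if the analysis allows for that choice. Here the only enrolled persons free of all three study conditions are eligible because a family member is affected. Their relatives are then enriched for disease by the entry rule itself. The specimen donors, who are not chosen on family history, have no family data.

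The resulting number would mix true aggregation with selection. Real aggregation could be hidden or reversed. If case families are more heavily selected than reference families, aggregation could appear where there is none. The protocol would still present the number as a measure of the strength of familial aggregation.

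**Working it through.** The protocol gives no disease rate, family size or expected OR, so there is no stated figure to reproduce. The check has two parts.

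**1. Possible sources of the denominator**

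| Candidate reference | Family data? | Selected on family history by the entry rule? | Usable as written? |
|---|---|---|---|
| Leftover-tube donors | None, and no contact | No | No |
| Enrollees free of CCM, stroke and epilepsy | Yes, by interview | Yes, through an affected family member | No, not without correction |
| CCM or epilepsy patients without stroke | Yes, by interview | No, they qualify on their own codes | Not named; carry a study condition, so not comparable with unaffected persons |

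For the second row the inflation is not automatic. It arises when the qualifying member is first-degree and has the disease counted as the outcome. A cousin, or a sibling with epilepsy only, does not raise first-degree stroke odds through the entry rule.

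**2. Illustration of size**

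Assumptions, none from the documents: n = 5 first-degree relatives, each with risk p = 0.05; no true aggregation (OR = 1); f = share of reference persons who entered through a first-degree relative with the outcome disease; g = the corresponding share of cases.

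Risk per relative, given at least one of n affected:

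c = p / (1 − (1 − p)^n) = 0.05 / (1 − 0.7738) = 0.221

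Observed OR = odds(g·c + (1 − g)·p) / odds(f·c + (1 − f)·p)

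With unselected cases (g = 0) the numerator is 0.05/0.95 = 0.0526.

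- f = 0.25: reference risk 0.25 × 0.221 + 0.75 × 0.05 = 0.0928; odds 0.1022; OR = 0.0526/0.1022 = 0.51.
- f = 0.5: reference risk 0.1355; odds 0.1568; OR = 0.0526/0.1568 = 0.34.

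For p from 0.01 to 0.10 and 3 to 6 relatives, still with g = 0, the null OR runs from 0.10 to 0.75 at f = 0.25 and from 0.05 to 0.60 at f = 0.5.

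If some case families are selected too, the direction is open. At n = 5 and p = 0.05:

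- g = 0.25, f = 0.5: 0.1022/0.1568 = 0.65
- g = f: 1.0
- g = 0.5, f = 0.25: 0.1568/0.1022 = 1.53

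**3. Does removing the qualifying relative repair it?**

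- *Family reached through one index patient.* With that patient counted, the reference risk is (1 + 4 × 0.05)/5 = 0.24. With that patient removed it returns to 0.05, the right value.
- *Any affected relative could have qualified the person.* The expected number affected, given at least one, is 5 × 0.05/0.2262 = 1.105. Removing one leaves (1.105 − 1)/4 = 0.026 instead of 0.05. A null OR against unselected cases then reads (0.05/0.95)/(0.026/0.974), or 1.95 before rounding. Simple removal over-corrects.

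**The case against.** - **The unseen analysis plan.** It may exist and could define affected status, exclude probands or correct for ascertainment. This stands in part: the absence of a correction here is not a finding in itself. But an analysis plan cannot create family histories for donors who will not be contacted, and it cannot change who was eligible.
- **Patients without stroke.** The stated aim is aggregation of stroke, so CCM or epilepsy patients without stroke could be called unaffected. They enter on their own codes, so a reader who infers that every possible reference person is selected on family history goes too far. For this group the problem is comparability, and the protocol does not name them as the reference.
- **Selection of cases.** A reader might infer from the multiply affected families that cases are selected as heavily as the reference. The sequencing section describes families already collected, sporadic cases are also recruited, and affected siblings may reflect real aggregation. Some case-side selection is plausible, but its extent is unknown.
- **The figures.** All inputs are assumed, and kinship is not restricted at entry, so f may be small. This stands: the numbers show sensitivity and are not an estimate for this study.
- **Reach.** Familial aggregation is not among the Specific Objectives or in the Hypothesis, which concern loci and biomarkers. This limits the importance of the point, but the OR is still planned and labelled.

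**Conclusion.** The point holds for the reference group. As written, the OR cannot be validly estimated as the familial risk ratio, because no source of unaffected persons combines family data, freedom from selection on family history and comparability. This follows from the protocol's own rules on eligibility and control samples and needs no numerical assumption.

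The size and direction of the bias are not determined. A null OR reading 0.51 or 0.34 depends on 5 relatives, 5% risk, unselected cases, and 25% or 50% of reference persons entering through a first-degree relative with the outcome disease. A reader might infer that the OR must be biased downward, or that true aggregation will be reversed. The documents support neither, since case-side selection could offset or outweigh the effect. The point should be fixed, but it does not touch the study's stated objectives.

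**What to change.** In the Statistical Analysis Strategy, do not report this OR as the familial risk ratio. Choose one:

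- **A.** Drop the OR. Keep the already planned cumulative incidence of stroke in first-degree relatives, labelled as descriptive of the enrolled families.
- **B.** Keep the OR only as a descriptive within-sample contrast. Define affected status (stroke, or any of CCM, stroke and epilepsy) and use a family-based analysis corrected for ascertainment.

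Under either option:

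- Where the family was reached through one index patient, do not count that patient as an affected relative.
- Where any affected relative could have qualified the person, condition on ascertainment; do not simply remove one relative.
- State that the leftover-tube controls are not used for this aim.

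**Cost.** One relative measure is lost (A) or becomes less precise (B). The relative through whom each person entered must be recorded; the questionnaire is not shown and may already capture this. No new samples are needed. A new reference group not selected on family history would require new interviews or external rates, and is not part of this fix.

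### The two-sided 0.05 cutoff is set for every p-value and is not limited to the familial-aggregation and Cox models, so as worded it would also govern any exome-wide or proteomic test

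*Protocol*

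**What the plan says.** The Statistical Analysis Strategy is the protocol's only statistical section. It opens broadly: "The statistical analysis for a genetic mutation in the Hispanic population will be performed using SAS software". It then describes odds ratios from stratified analysis and unconditional logistic regression for familial aggregation, Cox models for the relative risk of stroke, and cumulative incidence in first-degree relatives. It ends: "All p-values will be two-sided, with the significance level cutoff at $p < 0.05". The protocol states no other significance level.

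The aims are wider than those models. Section B says: "The objective of this research is to identify new genetic loci and validate novel serum biomarkers we recently identified for CCMs". The section on next-generation sequencing plans whole-exome sequencing, on the hypothesis that "some causative alleles for CCMs are rare genetic variants located in the unknown genetic loci". The section on serum/plasma biomarker discovery plans to validate the candidates from the mouse work and also to look for new markers by proteomics. There are five candidates: progesterone, and "four more biomarkers (Serpin A6, IL-12, IL-6, and Albumin) are all associated with PRG homeostasis/biogenesis in serum".

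On numbers, the Study Design gives "Up to 900 CCM Patients (between both Standard of Care and Research only samples"), which is a ceiling, and the section on control samples gives 1,000 control specimens. Nucleic acids and proteins from the controls "will be stored in MSBI in our -80 freezers until ready for analysis", but the protocol does not say whether they will be sequenced.

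**The concern.** A flat 0.05 is a normal choice for a few prespecified regression models. It does not suit a search over many genes or proteins, where the expected number of chance findings grows with the number of tests. The sentence covers all p-values, in a section that opens with mutation analysis, in a study whose stated purpose is to find new loci and markers. Taken literally, it fixes the wrong threshold for the study's main aims.

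At stake is how a nominal hit is read. Section A says "only three loci have been identified in CCM patients", so few further true loci can be expected, and in a large case-control comparison chance hits could outnumber them. The sentence would also contradict any separate analysis plan that sets a stricter threshold.

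**Working it through.** **Inputs from the protocol.** Two-sided cutoff 0.05; up to 900 patients; 1,000 control specimens; five candidate markers; three known loci.

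**Assumptions, because the protocol gives no figure.** 200 to 3,000 proteins; 20,000 genes, all null; carrier frequency per gene of 0.2%, 0.5% or 1%; controls sequenced; unrelated subjects; two-sided Fisher test per gene; 3 to 20 further true loci, all detected; groups of 300 as a smaller scenario, since 900 is a ceiling.

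**The stated figure.** The 0.05 is a chosen threshold, so there is nothing to derive: a valid test of a true null passes with probability up to 0.05.

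**Proteins.** Expected chance hits = 0.05 × number of tests: 0.05 × 200 = 10; 0.05 × 3,000 = 150.

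**Genes.** With rare carriers the Fisher test is conservative, so the flat 5% (0.05 × 20,000 = 1,000 genes) would overstate the count. The true size is the sum, over all pairs of carrier counts in cases and controls, of the binomial probability of the pair where the Fisher p-value is below 0.05. Multiplied by 20,000:

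| Cases v controls | 0.2% carriers | 0.5% carriers | 1% carriers |
|---|---|---|---|
| 900 v 1,000 | 0.0087 (173 genes) | 0.0303 (607) | 0.0370 (740) |
| 300 v 1,000 | 0.0103 (207) | 0.0208 (417) | 0.0326 (651) |
| 300 v 300 | 0.00004 (about 1) | 0.0020 (41) | 0.0120 (241) |

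**Share of hits that are true** = true loci / (true loci + chance hits).
- 900 v 1,000: from 3/(3 + 740) = 0.4% to 20/(20 + 173) = 10.4%.
- 300 v 300 at 0.2%: from 3/(3 + 0.8) = 79% to 20/(20 + 0.8) = 96%.
- 300 v 300 at 0.5%: up to 20/(20 + 41) = 33%.

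Chance hits exceed 20 in eight of the nine cells. The exception is 300 v 300 at 0.2%.

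**Five named markers, each tested at 0.05.** Chance of at least one false positive: at most 5 × 0.05 = 25%; 1 − 0.95^5 = 22.6% if independent. For equicorrelated normal statistics it is 18.3% at correlation 0.5 and 12.7% at 0.8.

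**Effect of a corrected threshold.** 0.05/20,000 = 2.5e-6. For a gene with no carriers among 1,000 controls, the case carriers needed are:
- 900 cases: from 5 (p = 0.024; 4 gives 0.0502) to 18 (p = 1.3e-6; 17 gives 2.8e-6).
- 300 cases: from 3 (p = 0.012) to 9 (p = 1.7e-6).

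**Holm for the five markers.** The first step is at 0.05/5 = 0.01. A comparison with 80% power at 0.05 has power P(Z > 2.576 − 2.802) = 59% there, and the detectable effect is (2.576 + 0.842)/(1.960 + 0.842) = 1.22 times as large.

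**The case against.** The best defence is that the sentence refers to the models just before it. It follows a statement that all models are adjusted for matching variables, and the section details only family-history, Cox and incidence analyses. The exome work is described elsewhere as assembly, variant detection and bioinformatics, in small families with affected siblings, where filtering may give no p-value at all. Multiplicity rules are also commonly left to an analysis plan, which is not shown here.

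Much of this stands. The narrow reading is possible, and it is why the harm is conditional. It does not remove the point: the section opens with mutation analysis, the words cover every p-value, and nothing narrows them. The objection is to a rule that is stated too broadly, not to an absent multiplicity plan.

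A reader might infer two stronger claims, and the protocol supports neither.
- *The study will test every gene at 0.05.* No such test is named, and sequencing of the controls is not stated.
- *Most gene hits would be chance results whatever the sample size.* At 300 v 300 and 0.2% carriers there would be only about one chance hit.

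The gene counts also assume unrelated subjects, while the study invites relatives. Ignoring relatedness could push the error rate above 5%, so the table is an illustration, not a forecast.

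**Conclusion.** The point holds as a defect of scope. The wording applies a flat 0.05 to any exome-wide or proteomic test, and that threshold is unsuitable there. It is acceptable for the familial-aggregation models and for Cox models of prespecified clinical or family-history exposures. The protocol leaves the Cox exposure open; if it were a variant or a protein, the same problem would arise.

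The size depends on whether per-gene or per-protein tests are run, on how many, and on the group sizes. At 900 v 1,000 under the stated assumptions, chance hits would clearly outnumber 3 to 20 true loci; in the smallest scenario they would not. For the five markers the risk is modest. Severity is minor to should-fix: minor if a separate plan already sets the thresholds, should-fix if this sentence is the only rule.

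**What to change.** Replace the sentence with text such as:

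> The two-sided 0.05 level applies to the familial-aggregation analyses, to Cox models of prespecified clinical or family-history exposures, and to each of the five prespecified candidate markers (with Holm adjustment as an option). Any exome-wide association test will be judged at a level corrected for the number of genes or variants tested (for example 0.05 divided by that number), and proteomic discovery will control the false discovery rate (for example Benjamini-Hochberg at 5%), whatever model produces the p-value.

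If a separate analysis plan already sets these thresholds, a clause limiting the scope of the 0.05 and a cross-reference to that plan are enough.

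The change is one sentence and needs no new data. The price is fewer nominal hits and lower power per test, of the size shown in the working. The power loss for the five markers arises only if Holm is chosen. The rule should be fixed before the sequencing and proteomic results are analysed, so that the threshold is not chosen with results in view.
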